## Research Question and Aims

**Specific Aim #1: Quantify 4DCT wrist biomarkers during resisted and unresisted tasks in healthy controls.** Healthy controls without any history of wrist injury or diseases will be scanned using 4DCT during wrist movement to characterize gapping at the scapholunate, radiolunate, and radioscapheoid joints (“radiocarpal joint and scapholunate interval”) as well as at the scaphotrapezium, scaphotrapezoid, and trapezotrapezoid joints (“scaphotrapeziotrapezoid [STT] joint”), as well as any other wrist joints captured within the imaging fields-of-view (i.e., trapeziometacarpal [TMC] joint). The existing device used to hold and guide subject’s wrists will be modified to provide resistance to movements. The scientific premise for this aim is our pilot cadaveric and patient imaging using 4DCT.

**Hypothesis:** *Scapholunate distances and bilateral asymmetry will be greater in the resisted tasks as compared to the unresisted tasks in both male and female subjects. Secondarily, gapping in females will be greater than males.*

## Study Design and Methods

### Methods:

#### 4DCT Imaging

A research CT scanner (Siemens NAEOTOM Alpha) or another dual source CT scanner will be used for imaging. Two independent but identical x-ray tubes are mounted on a rotating gantry at a 94 degree offset, with respective detector arrays opposing them. 4D (3D + time) CT imaging acquires high-temporal resolution, continuous or intermittent images over the width of the detector array in the superior-inferior direction. A bilateral static CT scan of the left and right wrist will first be performed. After that, four dynamic CT scans (4DCT) will be performed, two on each wrist, while patients are performing one of three types of movements: 1) passive and active grip; 2) unresisted and resisted flexion-extension; 3) unresisted and resisted radial-ulnar deviation. The passive/unresisted movements account for one dynamic CT scan and the active/resisted movements account for the second dynamic CT scan, for each wrist, for a total of 4 dynamic CT scans. In all conditions, the forearm will be restrained in a padded support channel to prevent upper arm movement and limit shoulder motion without affecting wrist and hand movement. Tasks will be performed using an ambidextrous, multipurpose mechanical device that will guide the left or right hand through the prescribed motion. Light resistance loading, which can be enabled or disabled, will be generated during hand motion. This custom device will consist of a single hand restraint or grip, a low-friction linear stage, a spring-loaded resistance mechanism, and a base, all made of plastic. For the dynamic scans, sequential, dual-source scanning mode is used which is similar to CT perfusion imaging. In this mode, imaging data of a moving joint are continuously acquired without table translation. Two seconds of

data will be acquired for each movement (full cycles of open/closed active grip, flexion-extension, or radial-ulnar deviation).

### **Image processing**

Seventeen image volumes will be reconstructed over the 2 second cycle using the commercially implemented dual-source cardiac reconstruction algorithm, resulting in a voxel dimension of 0.234 x 0.234 x 0.600 mm. 3D images of each of the 17 volumes, which are evenly distributed (temporally) across the motion cycle, will be generated using volume rendering techniques (VRT) and 4D movies will be made using the scanner's image processing workstation. All images will be stored in DICOM format for determination of metrics and biomarkers. All of the DICOM volumes will be processed using Analyze Pro (Mayo Foundation of Medical Education and Research), Cloud Compare, Mesh Lab, and existing software previously developed by our study team in Matlab (Mathworks, Inc.) platforms. Three-dimensional bone shape analysis will be conducted using open-source ShapeWorks software developed at University of Utah (<https://www.sci.utah.edu/software/shapeworks.html>).

### **Aim 1:**

Bilateral 4DCT scans will be performed on 30 healthy controls (15 males, 15 females) without any history of wrist injury or disease. Subjects will be randomly assigned to one of three groups of 10 subjects using stratified randomization to ensure equal distribution of sex in each group (5 males, 5 females); order of testing (unresisted and resisted) will be randomized within each group. 4DCT wrist data will be obtained while subjects in each group perform one of the following tasks through a full range of motion, bilaterally: 1) passive and active grip; 2) unresisted and resisted flexion-extension; and 3) unresisted and resisted radial-ulnar deviation. Subjects in group 1 will perform the task with the wrist in neutral position. Auditory cues will be given to subjects in all groups via metronome to ensure the full motion cycle is performed in 2 seconds (length of each individual scan). Resistance will be standardized across participants. The dynamic image sequence will be processed using existing software tools to obtain metrics quantifying the size and location of gapping (palmar or dorsal) at the scapholunate, radiolunate, and radioscaphoid joints as well as at the scaphotrapezium, scaphotrapezoid, and trapezotrapezoid joints—as well as any other wrist joints that may be captured in the imaging field-of-view—during the movement cycles.

### Subject Information

Target accrual: 31 healthy control subjects; up to 15 Mayo Clinic Hand Division surgeons

Subject population (children, adults, groups):

Control subjects without any history of wrist injury or disease will be recruited.

Exclusion Criteria:

Exclusion criteria which will be applied to both wrists for control subjects are as follows:

- 1) previously-diagnosed rheumatological conditions or connective tissue diseases;
- 2) inability to be appropriately positioned in the scanner for the imaging;
- 3) congenital malformations of the wrist or forearm;
- 4) diagnosed wrist osteoarthritis
- 5) age under 18 or over 60.

### Research Activity

Check all that apply and complete the appropriate sections as instructed.

1.  **Drug & Device:** Drugs for which an investigational new drug application is not required. Device for which (i) an investigational device exemption application is not required; or the medical device is cleared/approved for marketing and being used in accordance with its cleared/approved labeling. (Specify in the Methods section)
2.  **Blood:** Collection of blood samples by finger stick, heel stick, ear stick, or venipuncture.
3.  **Biological specimens other than blood:** Prospective collection of human biological specimens by noninvasive means that may include: urine, sweat, saliva, buccal scraping, oral/anal/vaginal swab, sputum, hair and nail clippings, etc.
4.  **Tests & Procedures:** Collection of data through noninvasive tests and procedures routinely employed in clinical practice that may include: MRI, surface EEG, echo, ultrasound, moderate exercise, muscular strength & flexibility testing, biometrics, cognition testing, eye exam, etc. (Specify in the Methods section)
5.  **Data** (medical record, images, or specimens): Research involving use of existing and/or prospectively collected data.
6.  **Digital Record:** Collection of electronic data from voice, video, digital, or image recording. (Specify in the Methods section)

7.  **Survey, Interview, Focus Group:** Research on individual or group characteristics or behavior, survey, interview, oral history, focus group, program evaluation, etc. (Specify in the Methods section)

NIH has issued a *Certificate of Confidentiality* (COC). *When checked, provide the institution and investigator named on the COC and explain why one was requested.* \_\_\_\_\_

#### Review of medical records, images, specimens – Category 5

**For review of existing data:** provide a date range or an end date for when the data was generated. The end date can be the date this application was submitted to the IRB. Example: *01/01/1999 to 12/31/2015* or all records through *mm/dd/yyyy*.

**Date Range:** Check all that apply (data includes medical records, images, specimens).

(5a) Only data that exists before the IRB submission date will be collected.

(5b) The study involves data that exist at the time of IRB submission **and** data that will be generated after IRB submission. Include this activity in the Methods section.

Examples

- The study plans to conduct a retrospective chart review and ask subjects to complete a questionnaire.
- The study plans to include subjects previously diagnosed with a specific disease and add newly diagnosed subjects in the future.

(5c) The study will use data that have been collected under another IRB protocol. Include in the Methods section and enter the IRB number from which the research material will be obtained. *When appropriate, note when subjects have provided consent for future use of their data and/or specimens as described in this protocol.*

Enter one IRB number per line, add more lines as needed

Data  Specimens  Data & Specimens \_\_\_\_\_

Data  Specimens  Data & Specimens \_\_\_\_\_

Data  Specimens  Data & Specimens \_\_\_\_\_

(5d) This study will obtain data generated from other sources. Examples may include receiving data from participating sites or an external collaborator, accessing an external database or registry, etc. Explain the source and how the data will be used in the Methods section.

(6) Video audio recording: *Describe the plan to maintain subject privacy and data confidentiality, transcription, store or destroy, etc.*

## HIPAA Identifiers and Protected Health Information (PHI)

Protected health information is medical data that can be linked to the subject directly or through a combination of indirect identifiers.

Recording identifiers (including a code) during the conduct of the study allows you to return to the medical record or data source to delete duplicate subjects, check a missing or questionable entry, add new data points, etc. De-identified data is medical information that has been stripped of all HIPAA identifiers so that it cannot be linked back to the subject. De-identified data is **rarely** used in the conduct of a research study involving a chart review.

**Review the list of subject identifiers below and, if applicable, check the box next to each HIPAA identifier being recorded at the time of data collection or abstraction.** Identifiers apply to any subject enrolled in the study including Mayo Clinic staff, patients and their relatives and household members.

**Internal** refers to the subject's identifier that will be recorded at Mayo Clinic by the study staff.

**External** refers to the subject's identifier that will be shared outside of Mayo Clinic.

Check all that apply:	INTERNAL	EXTERNAL
Name	X	
Mayo Clinic medical record or patient registration number, lab accession, specimen or radiologic image number	X	
Subject ID, subject code or any other person-specific unique identifying number, characteristic or code that can link the subject to their medical data	X	X
Dates: All elements of dates [month, day, and year] directly related to an individual, their birth date, date of death, date of diagnosis, etc.	X	
Note: Recording a year only is not a unique identifier.		
Social Security number	X	
Medical device identifiers and serial numbers		
Biometric identifiers, including finger and voice prints, full face photographic images and any comparable images		
Web Universal Resource Locators (URLs), Internet Protocol (IP) address numbers, email address	X	
Street address, city, county, precinct, zip code, and their equivalent geocodes	X	
Phone or fax numbers	X	
Account, member, certificate or professional license numbers, health beneficiary numbers		
Vehicle identifiers and serial numbers, including license plate numbers		
Check 'None' when none of the identifiers listed above will be recorded, maintained, or shared during the conduct of this study. (exempt category 4)	 None	 None

## Data Analysis

## Data Analysis Plan:

### **Aim 1:**

Normalized volar/dorsal location of the gapping at the scapholunate, radioscapoid, and radiolunate joints as well as the scaphotrapezium, scaphotrapezoid, and trapezotrapezoid joints—as well as other wrist joints in the acquired field-of-view—for the 15 male and 15 female subjects will be analyzed. Three-dimensional bone shape variations will be quantified. Magnitude and direction of contact center migration, bilaterally, will be analyzed during the 17 time steps during each movement. The primary assessment will be of the scapholunate distances as well as STT interosseous distances and bilateral asymmetry between the unresisted and resisted tasks in both male and female subjects. The secondary assessment will be of the scapholunate gapping as well as STT interosseous distance differences between males and females. The differences in bilateral migration of the contact center in the one limb as a percent normalization relative to the contralateral limb values will be determined and described using the t-distribution. These analyses will be repeated by sex, and other subgroups that become apparent during the study. With a sample size of 30, using a two-sided size 0.05 t-test, we will have 80% power to detect an effect size of 0.53 for the analysis of quantitative outcomes.

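### Must the plan fix in advance whether the male-female comparison of gapping is in millimetres or relative to bone size?

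*Combined protocol and SAP*

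**What the plan says.** The hypothesis under Research Question and Aims ends: "Secondarily, gapping in females will be greater than males". The Data Analysis Plan, Aim 1, turns this into the secondary assessment: "The secondary assessment will be of the scapholunate gapping as well as STT interosseous distance differences between males and females". The Methods text for Aim 1 says that both the size and the position of each gap will be measured. None of the three places attaches a unit to gap size or mentions division by, or adjustment for, bone size.

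Two other outcomes in the Data Analysis Plan do have a stated scale. One is "Normalized volar/dorsal location of the gapping", which concerns where the gap lies. The other is contact-center migration, expressed "as a percent normalization relative to the contralateral limb values", which scales to the opposite wrist and not to bone size. Bone shape is also to be quantified, but nothing ties it to the sex comparison. The only millimetre figure in the document is the voxel dimension under Image processing.

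The raw material for either scale will exist. Under 4DCT Imaging, "A bilateral static CT scan of the left and right wrist will first be performed", and under Image processing, "All images will be stored in DICOM format for determination of metrics and biomarkers".

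**The concern.** The comparison of men with women is between subjects, so a difference in bone size between the sexes does not cancel as it does when one wrist is compared with itself under two loads. Suppose male carpal bones are larger. If gaps do not grow with bone size, women have the same gap in millimetres but a larger one relative to their bones. If gaps grow in proportion to bone size, men have the larger gap in millimetres and there is no difference in relative terms. The hypothesis that women show greater gapping could then be supported on one scale and not on the other.

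With no scale declared, an analyst could in principle choose after seeing the data, and the relative scale leans towards the study's own prediction whenever gap size is unrelated to bone size. What is at stake is how the secondary sex result can be read.

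**Working it through.** **The plan's own figure.** The plan gives 80% power for an effect of 0.53 SD with N = 30 and a two-sided 0.05 t-test. For a paired or one-sample test the noncentrality is d × √n = 0.53 × √30 = 2.90 on 29 degrees of freedom, which gives power of 80.1%. The figure reproduces for a within-subject contrast. For 15 v 15 the noncentrality is d × √(15/2), so 80% power needs d = 1.06 (1.06 × 2.739 = 2.90). The sex comparison can therefore reliably detect only large differences on either scale.

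**How far the scale can move the result.** All inputs except 15 per sex and the two-sided 0.05 test are assumptions. Let r be female/male bone size, let g be the mean gap (male = 1), and let the coefficient of variation (CV) be the same in both sexes. The relative female mean is g/r. The pooled SD is CV × √((female mean² + male mean²)/2), and t = d/√(2/15) on 28 degrees of freedom.

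| g (female) | r | CV | Scale | Female v male mean | d | t | p |
|---|---|---|---|---|---|---|---|
| 1.00 | 0.85 | 20% | mm | 1.000 v 1.000 | 0.00 | 0.00 | 1.0 |
| 1.00 | 0.85 | 20% | relative | 1.176 v 1.000 | 0.81 | 2.21 | 0.035 |
| 0.90 | 0.80 | 15% | mm | 0.900 v 1.000 | -0.70 | -1.92 | 0.065 |
| 0.90 | 0.80 | 15% | relative | 1.125 v 1.000 | 0.78 | 2.14 | 0.041 |

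With a smaller size difference and a noisier gap (g = 1, r = 0.95, CV 30%), the relative means are 1.053 v 1.000. Then d = 0.053/(0.30 × √((1.053² + 1)/2)) = 0.053/0.308 = 0.17 and t = 0.47, so the choice of scale hardly matters.

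**How often the verdicts differ on the same data.** These are simulated, with 15 per sex.

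- With r from 0.80 to 0.95 and CV 15% to 30%, the verdicts differ in 5.5% to 96% of trials.
- With no sex effect beyond size, male bones 5%, 10% or 15% larger and CV 20% to 30%, they differ in 5-9%, 10-23% and 17-43%.
- With no sex effect beyond size, the same size differences and CV 40% to 50%, they differ in about 3-4%, 6-8% and 9-14%. A wider CV is plausible if the three task groups (5 men and 5 women each) are pooled.

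The document gives no size ratio, gap mean or CV with which to choose among these.

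**What the disagreement means.** If gaps do not depend on bone size, women do have the greater gap relative to size, and a relative test that finds it is right. If gaps are proportional to size, men do have the greater gap in millimetres, and a test in millimetres that finds it is right. The percentages count trials in which two different questions receive different answers. They are not false-positive rates of either test.

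**Which reading the text supports.** Where the analysis section rescales a quantity, it says so: once for gap location and once for contact-center migration. For the sex comparison it names gapping and an interosseous distance with no qualifier, and the primary assessment uses the word distance for the scapholunate joint in the same way. No sentence divides a gap by a bone dimension.

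**What adjustment would buy.** A model with sex and bone size as covariates keeps error at 2.3-2.7% in each direction. For a female excess of 1.06 SD beyond size, its power is 69-75%, 50-65% and 35-54% for male bones 5%, 10% and 15% larger. The unadjusted test in millimetres has 80% if gap is unrelated to size, and 48-62%, 25-43% and 11-27% if gap is proportional to size. Neither model is better throughout, and the document names no bone-size output to adjust for.

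**The case for a change.** The best case for a change is that a directional hypothesis deserves a declared scale. Millimetres may be the natural default, but the plan never says so. Because it rescales other measures in the same paragraph and also quantifies bone shape, a reader could think both scales are open. Writing down the unit takes a few words, and a scale named beforehand removes a choice that naming it afterwards cannot remove.

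Part of this stands. The unit is indeed unstated, the two scales can diverge, and one sentence would cost nothing. But the mixed use of normalization points the other way: explicit rescaling elsewhere makes an unqualified distance more clearly a length. An investigator who reported only a size-relative sex difference would be departing visibly from the text, and a reader holding the plan could see it. The stored images allow the other scale to be calculated at any time. Going further and prescribing a bone-size ratio or covariate would settle a scientific question on which statisticians reasonably differ, since sex and bone size are correlated and adjustment may remove part of what the hypothesis is about.

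**Conclusion.** The concern identifies missing detail and does not show a flaw in the analysis. Read in the ordinary way, the sex comparison is of lengths, and carrying it out in millimetres gives a sound answer to the question whether gaps are larger in women. The possible divergence between scales runs from negligible to large, entirely according to assumed bone-size ratios and gap variability, so no expected rate can be attached to it. It is confined to a secondary comparison of 15 v 15 healthy volunteers, where 80% power requires a difference of about 1.06 SD. The resisted-unresisted contrast compares each subject with himself or herself, so bone size is the same on both sides. Analysts can be expected to report the unit with the result, and a size-relative description can be added from the retained images if it is wanted. No change to the plan is needed.

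### The male-female comparison has no term for task; if run as a plain two-sample t-test, its confidence interval is too wide wherever the three tasks differ

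*Combined protocol and SAP*

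**What the plan says.** The secondary assessment is described in one sentence of the Data Analysis Plan, Aim 1: "The secondary assessment will be of the scapholunate gapping as well as STT interosseous distance differences between males and females". The population is given as subjects: distances "for the 15 male and 15 female subjects will be analyzed". No test, model or covariate is attached to this comparison. The only test in the plan is in the power statement: "With a sample size of 30, using a two-sided size 0.05 t-test, we will have 80% power to detect an effect size of 0.53".

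The design is in Study Design and Methods, Aim 1. Subjects are randomised to "one of three groups of 10 subjects using stratified randomization to ensure equal distribution of sex in each group (5 males, 5 females". Each group performs one task only: grip, flexion-extension or radial-ulnar deviation. Task is therefore a between-subject factor, and sex is balanced within it by design. Under 4DCT Imaging, each subject has repeated measurements: "four dynamic CT scans (4DCT) will be performed, two on each wrist". The plan does not say which wrist or load condition, or which average of them, enters the sex comparison.

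**The concern.** The trial stratifies so that sex is balanced within task, but the analysis plan does not use that structure. With 5 of each sex in every task group, the task effects cancel from the difference between the male and female means. They do not cancel from the pooled variance of a two-sample t-test, which treats a grip subject and a flexion-extension subject of the same sex as replicates. If typical gaps differ between motions, that spread is counted as noise. The estimated standard error then exceeds the true one, the interval is too wide and power falls.

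The resisted-versus-unresisted contrast is largely protected, because each subject's task level drops out of a within-subject difference. The sex contrast on distances has no such protection. It is also the comparison with least precision to spare, being 15 against 15.

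**Working it through.** **Inputs from the documents.** 30 subjects; 15 male and 15 female; three tasks, one per subject; 5 of each sex per task; two-sided alpha 0.05; 80% power; stated effect size 0.53.

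**Assumed.** k, the SD (divisor 3) of the three task means in units of the within-task SD. The documents give no task means or SDs, so k is varied from 0 to 1. Task means are set at -1.22k, 0 and +1.22k, within-cell SD is 1, data are normal, and there is one value per subject.

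**1. The plan's own figure.** By the noncentral t distribution, a one-sample or paired t-test with n = 30 (29 df) has 80.1% power at 0.53, and its detectable effect is 0.529. The stated figure reproduces in that form. For 15 v 15 (28 df) the detectable effect is 1.06, and power at 0.53 is 28.8%. The 0.53 therefore does not describe the sex comparison.

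**2. True standard error of the sex difference.** Task effects cancel under 5:5 balance, so the SE is sqrt(1/15 + 1/15) = sqrt(2/15) = 0.365, whatever k is. Simulation gives 0.364 to 0.367 at every k tried.

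**3. What the plain t-test estimates.** Within each sex, the expected sum of squares is 14 + 5 × 3k² = 14 + 15k². Over both sexes, divided by 28 df, the expected pooled variance is 1 + (30/28)k². The estimated SE is therefore too large by a factor of about sqrt(1 + (30/28)k²). At k = 0.5, for example, this is sqrt(1 + 1.071 × 0.25) = sqrt(1.268) = 1.126.

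**4. With task in the model.** Sex + task leaves 30 - 1 - 1 - 2 = 26 error df, and the residual variance has expectation 1 at every k. The mean 95% CI half-width is 0.743 and the detectable difference is 1.063 within-task SD. With 28 df and no task differences it is 1.060.

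**5. Simulation, plain t-test (28 df) against sex + task (26 df), 100,000 runs per setting.** Power is at a sex difference of 1.06 within-task SD.

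| k (assumed) | SE factor, step 3 | Mean half-width, plain | Mean half-width, sex + task | Power, plain | Power, sex + task |
|---|---|---|---|---|---|
| 0 | 1.00 | 0.741 | 0.743 | 80% | 80% |
| 0.25 | 1.03 | 0.766 | 0.743 | 78% | 80% |
| 0.5 | 1.13 | 0.835 | 0.743 | 72% | 80% |
| 0.75 | 1.27 | 0.939 | 0.743 | 62% | 80% |
| 1 | 1.44 | 1.070 | 0.744 | 49% | 80% |

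The true type I error of the plain test falls to about 4%, 3%, 1.4% and 0.5% at k = 0.25, 0.5, 0.75 and 1. With task in the model it stays at about 5%. A repeat with 400,000 runs per setting gave the same picture.

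**The case against.** **The plan does not assign a t-test to the sex comparison.** This is correct and limits the claim. The words "using a two-sided size 0.05 t-test" occur only in the power sentence, whose figure matches a one-sample or paired test. A reader might infer that an unadjusted two-sample t-test is prespecified; the documents do not say so. What stands is that no other test is named, no task term appears, and the natural default for 15 v 15 is the analysis examined above. The remedy is the same whichever analysis was intended.

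**The size is unknown.** Also correct. At k = 0 nothing is lost, and at k = 0.25 the interval is only 3% wider. How the 17 time points become one distance is not defined either, so k cannot be bounded from the documents. Different task means are plausible because the three motions differ, but that is a judgement.

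**A conservative test does no harm.** It produces no excess of false claims, and the estimate is unbiased. The loss is of precision and power in a secondary assessment. Adding task does not change the larger limitation that 15 v 15 detects about 1.06 SD.

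**Wrists or scans might be analysed as independent observations.** With four dynamic scans per subject and no stated unit of analysis, a reader might infer this, and conclude that the error is understated. The documents do not support it: the plan counts 30 subjects, 15 of each sex, and nowhere proposes 60 or 120 observations. The only consequence here is that the unit should be stated.

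**The 5:5 balance may not be exact.** The v4.2 addendum under Expert Consensus reports that half of the first subject's data was lost and that a replacement of the same sex and task is to be recruited. Balance is restored if the partial dataset is left out, and only slightly disturbed if it is kept.

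**Conclusion.** The point holds in conditional form. The plan compares the sexes without a task term, in a design where task is a between-subject factor balanced on sex. If that comparison is a plain two-sample t-test on one value per subject, the estimate is right but the interval is too wide by a factor of about sqrt(1 + (30/28)k²). That runs from no loss at k = 0 to 44% at k = 1, where power drops from 80% to about 49%.

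The conclusion rests on three things: the t-test being the method used, which is inferred; the value of k, which is assumed; and the outcome being a distance level. For a resisted-minus-unresisted change, only task differences in that change would inflate the error. The documents do not show that the error is understated or that a false positive is likely. This is an inexpensive improvement to a secondary analysis and does not affect the validity of the primary one.

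**What to change.** In the Data Analysis Plan, Aim 1, add after the sentence on the secondary assessment: the male-female comparison will use one value per subject (for example the mean over the two wrists, within each load condition or over both, as specified) in a linear model with sex and task group as factors (26 error df), and the sex difference will be reported with its 95% CI.

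A mixed model on scan-level data, with fixed sex, task, load and side and a random subject intercept, is an alternative. It gives the same answer when data are complete. The text should also say whether the first subject's partial dataset is included.

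The cost is one sentence and two error degrees of freedom (28 to 26). If the tasks turn out not to differ, the detectable difference moves from 1.060 to 1.063 within-task SD. No new data and no change to study conduct are needed.

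### The single power figure (80% at effect size 0.53) holds only for a paired test pooling all 30 subjects, not for the by-sex repeats or the male-female comparison, and no contrast tests whether the response to resistance differs by sex

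*Combined protocol and SAP*

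**What the plan says.** The hypothesis under Research Question and Aims is that scapholunate distances and bilateral asymmetry "will be greater in the resisted tasks as compared to the unresisted tasks in both male and female subjects"; a secondary hypothesis is that gapping is larger in females. The Data Analysis Plan for Aim 1 makes the resisted-unresisted contrast, in men and women, the primary assessment. It makes the male-female difference in scapholunate gapping and STT distance the secondary one. It then adds: "These analyses will be repeated by sex, and other subgroups that become apparent during the study".

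The only power statement assumes 30 subjects and a t-test at the two-sided 0.05 level, and claims: "we will have 80% power to detect an effect size of 0.53 for the analysis of quantitative outcomes". It does not say whether the test is paired or two-sample, and it gives no raw difference or SD.

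On numbers, the Aim 1 methods state "Bilateral 4DCT scans will be performed on 30 healthy controls (15 males, 15 females"), split into three movement groups of 10 with "equal distribution of sex in each group (5 males, 5 females"). Each subject does one movement under both conditions, in randomised order, with both wrists.

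**The concern.** The power sentence is worded to cover quantitative outcomes generally, yet the plan contains at least three kinds of comparison: resisted v unresisted within all subjects, the same contrast within each sex, and men v women. A t-test on 30 paired differences, one on 15 paired differences and a 15 v 15 two-sample test have very different power at the same standardised effect. A reader could take 80% at 0.53 to cover all three.

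A second gap sits beside this. The plan compares the sexes on the level of gapping. It has no contrast asking whether the change from unresisted to resisted differs between men and women. The by-sex repeats will place two sex-specific results side by side, and with 15 subjects each they can easily fall on opposite sides of 0.05 when the true effects are equal. The plan does not say how such a result would be interpreted.

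**Working it through.** **Inputs.** From the Data Analysis Plan: N = 30, two-sided alpha 0.05, effect size d = 0.53, power 80%. From the Aim 1 methods: 15 men, 15 women, each measured under both conditions. Assumption: one summary value per subject and condition, so that subjects are independent units.

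**Formulas.** Exact noncentral t; power = P(|T| > t_crit).
- Paired, n subjects: df = n − 1, noncentrality = d√n, with d in SDs of the within-subject change.
- Two-sample, n per sex: df = 2n − 2, noncentrality = d√(n/2), with d in between-subject SDs of whatever is compared (a level or a change).

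**Step 1: reproduce the stated figure.** Paired, n = 30: noncentrality 0.53 × √30 = 2.903, t_crit(29) = 2.045, power **80.1%**. The alternatives do not match: two-sample 15 v 15 gives 28.9%, two-sample 30 v 30 gives 52.3%, and a one-sided paired test gives 88.3%. The figure is therefore for a paired test on all 30 subjects, pooled over sex and movement.

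**Step 2: one sex alone.** Paired, n = 15: noncentrality 0.53 × √15 = 2.053, t_crit(14) = 2.145, power **48.1%**. For 80% power, d = **0.78**.

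**Step 3: men v women.** 15 v 15: noncentrality 0.53 × √7.5 = 1.451, t_crit(28) = 2.048, power **28.9%**. For 80% power, d = **1.06**. The same arithmetic applies to a sex difference in level and to one in response to resistance, but the SD differs: that of the level in the first case, that of the within-subject change in the second.

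**Step 4: both sexes significant, if that is required.** The sexes are independent groups, so with the same true d in each, joint power is the square of the per-sex power: 0.481² = **23.1%** at 0.53. For 80% joint power each sex needs √0.80 = 89.4%, which requires d = **0.89**.

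**Step 5: discordant by-sex results when the true effects are equal.** P(exactly one significant) = 2p(1 − p), where p is the per-sex power.

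| True d in both sexes | Per-sex power p | Both | Exactly one | Neither |
|---|---|---|---|---|
| 0.53 | 48.1% | 23.1% | 49.9% | 27.0% |
| 0.78 | 80% | 64% | 32% | 4% |
| 0.89 | 89% | 80% | 19% | 1% |

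**Step 6: precision of a condition-by-sex contrast.** Comparing per-subject changes, 15 v 15, the 95% CI half-width is 2.048 × √(2/15) = **0.75** SD of the paired change.

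**The case against.** The strongest reply is that the plan does not misstate anything: it says 30 subjects and makes no claim about 15. That stands as far as it goes; the figure is correct for the pooled paired test. But the sentence is attached to quantitative outcomes at large, and neither the by-sex repeats nor the secondary comparison has a power figure of its own.

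A reader might infer that the plan will judge sex differences by setting two p-values against each other. The documents do not support that. They list a direct male-female comparison as the secondary assessment and nowhere propose inference from discordant p-values. What remains is narrower: that comparison concerns the level of gapping, has no named test or model, and does not address whether the response to resistance differs by sex. No stated hypothesis requires that contrast, so it is needed only if the by-sex results are to be interpreted against each other.

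A reader might also infer that the trial has only 23% power for its primary hypothesis, or is likely to report a false effect in one sex only. Both go too far. The 23% applies only if each sex must be separately significant; the hypothesis can also be read as a pooled statement about a sample containing both sexes. The 50% discordance assumes a true effect of exactly 0.53 in each sex. That value is a detectable effect, not an expected one, and discordance falls to 32% at 0.78 and 19% at 0.89. The documents give no SD or raw effect from which to choose among these.

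Finally, the sentence about repeating analyses directly follows one on contact-centre migration, so it may be meant for that outcome alone. Applying it to the primary outcome is reasonable but not explicit. On the narrower reading, the plan gives no sex-specific analysis of the primary outcome at all.

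**Conclusion.** The point holds in this form. The 80% at 0.53 is right for one analysis, the paired comparison pooled over all 30 subjects. At that effect size the by-sex repeats have 48% power (detectable effect 0.78) and the planned male-female comparison has 29% (detectable effect 1.06 between-subject SD). Joint power of 23%, with a detectable effect of 0.89, applies only under the reading that each sex must reach significance, and the plan should say whether it intends that. The missing condition-by-sex contrast is a real but secondary gap.

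These figures rest on one value per subject and condition, a two-sided 0.05 test without multiplicity adjustment, and 15 analysable subjects per sex. They also pool three different movements: within one movement there are 5 per sex, where a paired test has 15% power at 0.53. The pooled primary comparison is not undermined.

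**What to change.** 1. State that 0.53 applies to the paired resisted-unresisted comparison pooled over all 30 subjects. Beside it give 0.78 (one sex), 0.89 (both sexes, if required) and 1.06 (between sexes), naming the SD to which each refers.
2. State whether the primary hypothesis is pooled or requires the effect in each sex separately.
3. Replace the by-sex repeats with one mixed model containing condition, sex, condition-by-sex and movement task, with subject and wrist as repeated levels.
4. From that model report the male-female difference in level, the condition-by-sex interaction and the sex-specific effects, each with a 95% CI. Do not infer a sex difference from one significant and one non-significant result.
5. Label any other subgroups exploratory.

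The cost is analysis-plan wording, with no extra subjects or scans. The downside is that the stated power looks less favourable and the interaction interval will be wide, about ±0.75 SD of the paired change. The model does not raise the sex-specific power materially; it makes the limits visible and tests the right contrast.
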